7.1.4 Suspected Unexpected Serious Adverse Reactions

Suspected unexpected serious adverse reactions (SUSARs) are serious events that are not listed in the latest approved Dysport IB or the lidocaine SmPC in the UK and that the investigator identifies as related to agent or IMP or procedure.

7.1.5 Pregnancy

Investigators are instructed to report any pregnancy within 24 hours of first awareness of the pregnancy. Information regarding any pregnancy must be collected on the AE page of the eCRF and also on the standard pregnancy outcome report form. Ipsen will request further information from the investigator concerning the course and the outcome of the pregnancy (including the medical condition of the mother, fetus and neonate) using the form.

Information received on any pregnancy with conception date within the time interval specified in the study protocol will be reported in the final clinical study report.

7.1.6 Adverse Events of Special Interest

The effects of Dysport and all BTX products may spread from the area of injection to produce symptoms consistent with BTX effects. These symptoms have been reported hours to weeks after injection. Remote spread of toxin that affects swallowing and breathing can be life threatening, and there have been reports of death. The risk of symptoms is increased in subjects who have underlying conditions (e.g. disorders of the neuromuscular junction) that would predispose them to these symptoms. Dysport is contraindicated in individuals with known hypersensitivity to any BTX preparation or to any of the components in the formulation. Adverse events of special interest (AESIs) for Dysport are AEs that suggest a possible remote spread of effect of the toxin or hypersensitivity. A list of preferred terms of AESIs will be provided in the statistical analysis plan (SAP). All AEs will be monitored by the sponsor to determine if they meet the criteria of AESIs. These AESIs will be further analysed to determine if there is a plausible possibility that they represent distant spread of toxin or hypersensitivity. In order to perform the analysis, variables including alternate aetiology (medical history, concomitant medication, or diagnosis which could account for the symptoms), location of Dysport administration, and temporal relationship to Dysport administration will be considered by the sponsor.

7.1.7 Deaths

All AEs resulting in death during the study period must be reported as a SAE.

The convention for recording death is as follows:

- AE term: Lead cause of death (e.g. multiple organ failure, pneumonia, myocardial infarction),
- Outcome: Fatal.

The only exception is if the cause of death is unknown (i.e. sudden or unexplained death), in which case the AE term may be “death” or “sudden death”.

7.1.8 Reporting to Competent Authorities, IECs/IRBs and other Investigators

The sponsor will ensure that processes are in place for submission of reports of SUSARs occurring during the study to the Competent Authorities (CAs), Independent Ethics Committees

(IECs)/Institutional Review Boards (IRBs) and other investigators concerned by the agent or IMP.

Reporting will be done in accordance with the applicable regulatory requirements.

The sponsor must report all SUSARs to European Medicines Agency's EudraVigilance database within 15 days. Fatal and life-threatening SUSARs should be reported within seven calendar days, with another eight days for completion of the report.

The sponsor can prepare additional reports for other authorities (e.g. FDA).

7.2 Specific Safety Assessments

The investigator is responsible to monitor subjects' safety at any time during the study.

For each assessment performed, the investigator must document his review of the result(s) in the source document(s). In case of abnormal result or value(s) falling outside of predefined normal ranges, the investigator should specify whether the finding is considered as "clinically significant" (CS) or "not clinically significant" (NCS).

Any finding, whether judged CS or NCS may lead to retest at the discretion of the investigator.

7.2.1 *Physical examinations*

Physical examinations including height, body weight, body temperature (only at screening) and pain description will be conducted as presented in the schedule of assessments in Section 18.1. Physical examination includes inspection of general appearance, skin, neck (including thyroid), eyes, ears, nose, throat, heart, lungs, abdomen, lymph nodes, vascular system, extremities, musculo-skeletal system and nervous system.

The nature of the scar pain will be assessed using standardised descriptors e.g. sharp, dull, aching, burning, shooting, stabbing, electric shocks.

Any changes from baseline in physical examination findings judged to be clinically significant by the investigator/ will be recorded as AEs. Any physical examination findings (abnormalities) persisting at the end of the study will be followed by the investigator until resolution or until reaching a clinically stable endpoint.

7.2.2 *Vital Signs*

Vital signs, including HR, SBP and DBP will be assessed as presented in the schedule of assessments in Section 18.1.

SBP, DBP and HR assessments will be performed with an automated device so that measurements are independent of the observer. These parameters will be recorded after at least 5 minutes rest in supine position for supine assessment, followed by 1 minute in sitting position before standing up where applicable. The standing assessment will be performed after at least 2 minutes standing (only at screening visit). The investigator will record any clinically significant abnormal value as AEs. All AEs will be discussed regularly with the sponsor.

7.2.3 *Electrocardiograms*

Twelve-lead computerised standard ECGs, with paper printout, will be obtained while the subject is in resting supine position for at least five minutes and until four regular consecutive

complexes are available, at the screening visit only as presented in the schedule of assessments in Section 18.1.

The ECG will be interpreted by a qualified physician at the CRU as soon after the time of ECG collection as possible, and ideally while the subject is still present, for immediate subject management. The qualified physician will document his review and interpretation (including evaluation of clinical significance in case of abnormality) on every ECG printout.

The paper printouts will be kept in the source documents at site. Only the interpretation and abnormalities will be reported in the eCRF for integration with other clinical study data. These paper ECGs may be subject to further review, if appropriate. The investigator will review each safety laboratory test results, document the review, and record any clinically significant abnormal value as AEs. All AEs will be discussed regularly with the sponsor.

7.2.4 Clinical laboratory tests

Blood and urine samples collection will be performed for standard clinical laboratory tests, including biochemistry, haematology, serology and urinalysis panels, as well as specific tests such as urine drug screening and urine pregnancy tests for women of childbearing potential, as indicated in the schedule of assessments in Section 18.1.

Full details related to the samples processing, labelling, storage, shipment and destruction procedures will be documented in a laboratory stand-alone document.

The results of laboratory tests performed during the screening phase must be obtained before injection test 1.

The investigator will review each safety laboratory test results, document the review, and record any clinically significant abnormal value as AEs. All AEs will be discussed regularly with the sponsor.

7.2.4.1 Blood Analyses

Parameters to be assessed are listed in Section 18.3.

7.2.4.2 Urinalysis

Freshly voided urine samples (at least 10 mL) will be collected to perform a dipstick assessment of the parameters listed in Section 18.3. In case of abnormal result on the dipstick, a confirmatory analysis or additional assessments might be requested to the local laboratory, at the discretion of the investigator.

Microscopy will be performed, if indicated, but results will not be collected in the eCRF. If in the opinion of the investigator there are any clinically significant abnormalities in microscopy, they will be recorded as an AE in the eCRF.

7.2.4.3 Pregnancy Test

Human chorionic gonadotrophin will be assessed using an urinary dipstick in all female subjects as specified in the schedule of assessments in Section 18.1. It may be repeated at any time during the study according to investigator's judgement.

7.2.4.4 Drug of Abuse

Urine drug screen testing will be performed as specified in Section 18.1 and at any time at the discretion of the investigator. If positive the subject may still continue in the study if there is a

clinically plausible reason for the result and no concerns by the investigator e.g. a positive opioid test due to the subject taking as prescribed an opioid containing compound as analgesic.

7.2.5 *Scar Ultrasound*

An ultrasound of the scar will be performed to exclude subjects exhibiting a neuroma in their scar-related painful area.

8 PHARMACOKINETIC ASSESSMENTS

Not applicable.

[figure not shown]
9 PHARMACODYNAMIC ASSESSMENTS

The following pharmacodynamic parameters will be collected and reviewed during the study at specific timepoints as described in the study schedule of assessments in Section 18.1.

9.1 Numerical Rating Scale

The NRS is a 11-point scale to assess subject pain perception as described in Figure 4. Subjects will be asked for their score.

Figure 4 Numerical Rating Scale

9.1.1 Spontaneous Average and Worst Pain NRS Score during the Screening Visit

Subjects will be asked to record their average scar-related pain intensity for the previous 24 hours. The subjects will be asked the following question:

“Please rate your pain by selecting the one number that best describes your pain on average during the last 24 hours.”

Subjects will be asked to record their worst scar-related pain intensity for the previous 24 hours. The subjects will be asked the following question:

“Please rate your pain by selecting the one number that best describes your pain at its worst during the last 24 hours.”

9.1.2 Spontaneous Current Pain NRS Score in Part A

On the day of the injection test, before the injection test (predose), subjects will be asked what are their current NRS score, the pain felt by the subject at the time of the assessment. The subjects will be asked to answer the following question:

“Please rate your pain by selecting the one number that best describes how much pain you have right now.”

Subjects will then be injected and will report their pain relief within 30 minutes after the injection test if any. Subjects will be asked for their current NRS score at 30 minutes and one hour post-injection test, according to the question just described previously.

Subjects will be provided with a paper diary after injection tests 1 and 2. They will be invited to record at home after discharge their current NRS scores hourly up to eight hours and between 20 and 24 hours post-injection test in this diary.

9.1.3 Spontaneous Average and Worst Pain NRS Score in Part B

If subjects are responders, they will be provided with an Actiwatch® during an Actiwatch® training visit to record their spontaneous NRS score at home. They will start NRS score recording from the training visit on Actiwatch® use.

The Actiwatch® will alarm and alert the subjects twice a day to record their average and maximal NRS scores over the preceding 12 hours. The questions will be asked of the subject by the Actiwatch®:

“Please rate your pain by selecting the one number that best describes your pain on average during the last 12 hours.”

“Please rate your pain by selecting the one number that best describes your pain at its worst during the last 12 hours.”

The Actiwatch® will allow electronic NRS score collection and storage from the Actiwatch® training to EoS. Data will be extracted from the Actiwatch® at each visit. A paper diary will also be provided to subjects in the unlikely event of an Actiwatch® malfunction during the collection period. One week before post-dosing visit to the CRU, the subjects might be requested to complete the paper diary as a quality control check for the data in the Actiwatch® and as a back up in case there is a problem with downloading information from the Actiwatch®.

9.2 Stimulus-evoked NRS Score during Quantitative Sensory Testing

Subjects will be submitted to stimuli of various nature applied to the painful area. Stimulus-evoked NRS score will be collected during the assessments.

Subjects will be asked what are their current NRS scores predose and post-stimulus.

At baseline and at the post-dose visits light touch, pressure and temperature will be used as stimuli for QST.

The QST battery of tests is described in full in Sections [18.4](#) and [18.5](#).

9.2.1 Light Touch

The surface of the painful area will be measured on radial spokes starting from the previously mapped painful area applying a von Frey filament. The filament will be applied until it slightly bends and be left in place for 4-5 seconds. Subjects will be asked to report when the von Frey filament first begins to cause any pain sensation and the distance of that point from the initial mapped painful area will be recorded.

The first painful position will be located on the skin and this process will be done for each radial spoke.

The resulting points will then be transferred onto a tracing paper sheet and connected to define the outline of the painful area submitted to light touch. The area of pain will be calculated by using 1 cm² squares on the tracing paper (see Section [9.3](#)).

9.2.2 Pressure (Pressure Pain Threshold)

An evoked current NRS score will be recorded for each pressure intensity. The pressure pain threshold (PPT) assesses the level of pressure causing pain. In post-surgical neuralgia subjects, light, normally non-painful pressure applied at the most painful point causes/may cause intense pain. The PPT is assessed by the investigator by using a pressure algometer (contact area 1 cm²), documented in the source data, and transferred to the eCRF. The threshold for pressure induced pain is measured and then repeated in three series of slowly increasing stimulus intensities (at a rate of about 50 kPa/s). The subject must not be able to look at the readings during the

measurement. For the final PPT, the arithmetic mean of all three consecutive measurements will be calculated (Maier et al., 2010; Mainka et al., 2014).

9.2.3 Temperature

A thermal stimulation will be provided from a thermode placed on the painful area.

The temperature of the thermode is controlled by a Medoc TSA II NeuroSensory Analyser (Medoc Ramat Yishai, Israel). The TSA-II – NeuroSensory Analyser is a precise, computer-controlled device capable of generating and documenting response to highly repeatable thermal and stimuli, such as warmth, cold, heat-induced pain and cold-induced pain. The thermal sensory testing element measures the thresholds for four sensory sub-modalities:

- Warm sensation, for normal subjects, usually at 1- 2°C above adaptation temperature (C fiber mediated sensation),
- Cold sensation, for normal subjects, usually at 1- 2°C below adaptation temperature (A-delta fibers mediated sensation),
- Heat induced pain, threshold around 45°C (mostly C fiber mediated sensation, with some involvement of A-delta fibers).

Cold induced pain, the most variable and difficult to assess of all previous modalities, at about 10° C (combination of both C and A-delta fiber mediated sensation). Warm detection and heat pain thresholds will be determined. The start of the temperature will be 32°C and gradually ramped by 1°C/sec. The heat pain threshold will be obtained when the subject will experience a painful feeling. The thermode will automatically shut down at a preset temperature of 53°C in order to avoid any tissue damage.

Cold detection and cold pain thresholds will also be determined, as programmed by the TSA II.

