
Pressure Pain Threshold (PPT): A hand-held pressure algometer (Algometer type II, Somedic Production AB, Sweden, diameter contact tip 10mm; cover 2mm thick rubber; standardised and constant speed of pressure increase of 0.3kg/s) is used to measure the PPT's in KPa (Kilo Pascal). The probe is placed perpendicular to the skin and standard incremental pressure is applied until the subject perceived the pressure as pain when the procedure is immediately terminated. At each site, a set of 3 measurements are taken at 4 different nearby points and an average PPT value is calculated from the 12 measurements. If the patient feels too uncomfortable then please restrict to fewest number of consistent readings (3 to 4).

Ischemic arm test to measure DNIC: DNIC is measured by inducing a heterotopic noxious conditioning stimulation. This is evoked by an inflated blood pressure cuff and thereby creating an ischaemic compression of the arm. Blood pressure cuff positioned on the arm was inflated above systolic pressure (200 mmHg) for 10 minutes, or until a Numerical Rating Scale of 6 was achieved. The point on the painful site with the lowest PPT value (average of 3 measurements) is chosen to measure the CPM response. A set of 3 PPT measurements are then taken at this point following which the cuff is deflated. The average of the 3 PPT measurements are taken.

Temperature Thresholds: This test measures the CDT, WDT, CPT and HPT and paradoxical heat sensation. Four sensory sub-modalities are measured using a computer-controlled thermode with surface area of 9 cm² which is connected to a patient-activated push-button (TSA-II Quantitative NeuroSensory Analyzer; Medoc, Ramat Yishai, Israel). The system contains a pre-loaded software which dictates the temperature changes. The baseline temperature is automatically set at 32 °C. The temperature then decreases at a constant rate of 1 °C /s until the subject perceived the thermode as cold and immediately pressed a push-button. Four consecutive measurements are taken with the thermode returning to baseline temperature each time. Similarly, HDT, is measured but with the temperature increased from 32°C. Subsequently, CPT and HPT are determined in a similar manner, and in that order but by taking an average of 3 consecutive measurements. To avoid thermal injury the thermode with automatically cut off at 0°C at the lower end and at 50°C at the higher end.

8. Termination of QST

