For each subject, the number of incorrect perception of temperature by test will be derived for the painful and non-painful area.

Temperatures below or equal to 0°C and temperatures above or equal to 50°C are not reliable for the analyses and therefore will be excluded from the statistical analyses.

5.7.4.2 *Main Secondary Analysis*

For each estimate, analysis will be based on the treatment policy estimand: No adjustment will be made in case of intake of rescue medication.

Painful Area Mapping

Summary table for raw data and changes from baseline of the longitudinal axis and the total painful area will be provided by treatment group and measurement time and Placebo versus all Dysport groups by measurement time.

Spontaneous NRS scores

Each analysis on the spontaneous NRS score will be produced separately for the Average Numeric Pain Rating and the Worst Numeric Pain Rating.

Summary table for raw data and changes from baseline in the spontaneous NRS score will be produced by treatment group, and measurement times, only for the daily average for the average NRS scores and for the daily worst for the worst NRS scores).

The graph of arithmetic mean \pm SD over time will be provided for the change from baseline in the spontaneous NRS score (daily average for the average NRS and the daily worst for the worst NRS) with all treatment groups on the same graph. Size groups at each time point will also be presented on the graph.

The graph of arithmetic mean \pm SD over time will be provided for the change from baseline for the morning score and evening score on the same graph, separately for each treatment group.

Individual raw data and change from baseline spontaneous NRS score versus time profiles will be presented graphically for each subject with the worst numeric pain rating within the last 12 hours and the average numeric pain rating within the last 12 hours on the same graph.

Listings of individual data of the spontaneous NRS scores will be provided including all subjects with missing data. Values measured on a day where a rescue medication was taken will be flagged.

Summary table for SPID and AUE parameters will be computed for each assessment, by treatment group and visit.

For each assessment, scatter plots and box whisker plots will be generated for the comparison of SPID and AUE between the treatment groups.

Listing of individuals values of SPID and AUE will be provided.

OST analyses

Baseline assessments

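### The thermode's automatic heat cut-off is 53°C in Protocol section 9.2.3 but 50°C in Attachment 4, and the SAP exclusion rule matches only the latter

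*Protocol*

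**What the plan says.** Protocol section 9.2.3 describes the thermal part of the quantitative sensory testing (QST). On the device: "The temperature of the thermode is controlled by a Medoc TSA II NeuroSensory Analyser". On where it is applied: "A thermal stimulation will be provided from a thermode placed on the painful area". On the ramp: "The start of the temperature will be 32°C and gradually ramped by 1°C/sec". On the upper limit: "The thermode will automatically shut down at a preset temperature of 53°C in order to avoid any tissue damage".

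Protocol section 9.2 introduces the tests and points onward: "The QST battery of tests is described in full in Sections" 18.4 and 18.5. Section 18.4 is Attachment 4, the site's own QST procedure. Its paragraph on temperature thresholds names the "TSA-II Quantitative NeuroSensory Analyzer; Medoc, Ramat Yishai, Israel", starts at 32°C, moves at 1°C/s, and closes: "To avoid thermal injury the thermode with automatically cut off at 0°C at the lower end and at 50°C at the higher end".

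SAP section 5.7.4.1, under thermal detection and pain thresholds, says: "Temperatures below or equal to 0°C and temperatures above or equal to 50°C are not reliable for the analyses", and removes such values from the statistical analyses. Section 5.7.4.2 counts the subjects concerned in a table of assessments not done, with a reason stating that the values were left out because a threshold was passed. The SAP nowhere mentions 53°C.

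**The concern.** Two parts of one protocol give different temperatures for the same automatic cut-off, and each justifies its figure as protection against injury. An operator or monitor checking the device against section 9.2.3 would accept a setting 3°C above the one that Attachment 4 ties to avoiding thermal injury. One checking against Attachment 4 would call the section 9.2.3 setting wrong. The heat goes onto a painful scar area, so the limit should be unambiguous.

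There is also a smaller consequence for analysis. The SAP exclusion point equals the Attachment 4 cut-off. If the device ran to 53°C, some of the values the SAP discards would be real threshold measurements, and the reason given in the table would misdescribe them.

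**Working it through.** No sample size, power or error-rate figure is involved. The check sets the texts side by side and adds one line of arithmetic.

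**Inputs**

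| Item | Protocol 9.2.3 | Protocol Attachment 4 (18.4) | SAP 5.7.4.1 and 5.7.4.2 |
|---|---|---|---|
| Device | Medoc TSA-II | Medoc TSA-II | not restated |
| Start temperature | 32°C | 32°C | not restated |
| Ramp | 1°C/s | 1°C/s | not restated |
| Upper limit | 53°C, automatic | 50°C, automatic | values ≥ 50°C dropped |
| Stated purpose | prevent tissue damage | prevent thermal injury | reliability of the values |

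**Step 1: are these two different quantities?** One might read 53°C as the device's maximum and 50°C as the test's stopping point. The wording does not allow it. Both are described as the temperature at which the thermode stops by itself, both serve to prevent injury, and both apply to the same device, start and ramp.

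**Step 2: is one of them superseded?** No. Attachment 6 shows that Amendment 2 edited abbreviations in the Attachment 4 temperature paragraph and left 50°C in place. It lists no change to section 9.2.3. The conflict is therefore between two pieces of current text, not between current text and the amendment record. The cross-reference in section 9.2 does not say which text governs if they differ.

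**Step 3: size.**

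- Difference in limit: 53 − 50 = 3°C.
- Time to reach a limit: (limit − 32°C) / (1°C/s).
- To 50°C: (50 − 32) / 1 = 18 s.
- To 53°C: (53 − 32) / 1 = 21 s.
- Extra heating under section 9.2.3: 21 − 18 = 3 s, all of it above the Attachment 4 limit.
- For scale, section 9.2.3 puts the heat-pain threshold at around 45°C: (45 − 32) / 1 = 13 s, before either limit.

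**Step 4: what the SAP rule does under each text.**

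- *Cut-off at 50°C.* A subject with no pain response before 50°C reaches the cut-off. No threshold has been found, the value is dropped, and the reason given in the table is accurate.
- *Cut-off at 53°C.* A subject who reports pain between 50°C and 53°C has a measured threshold below the device limit. The SAP still drops it and reports it as beyond a threshold, although the device had not reached its cut-off. These would be the highest heat-pain thresholds recorded.
- *Either way*, the heat readings analysed are those below 50°C. What changes is whether the dropped values are ramps that ran to the limit or include real measurements.

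**The case against.** The strongest reply is that the conflict is unlikely to affect many ramps. Attachment 4 gives the subject a push-button, section 9.2.3 takes the threshold when the subject feels pain, and the termination section of Attachment 4 lets the operator stop at the subject's request or for discomfort. At a threshold near 45°C a ramp ends well short of both limits. There is one site, Attachment 4 is that site's own procedure, and it says that pre-loaded software controls the temperature changes. All of this stands and limits the practical reach. It does not remove the contradiction, because a cut-off exists for the subject who does not respond in time.

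A reader might infer more than the documents support:

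- *That the cut-off is the only protection.* It is the only automatic heat limit described, but the push-button and operator termination are also safeguards.
- *That heat-pain readings would have different ceilings across visits.* The SAP drops everything at or above 50°C under either setting, so the analysed range is the same. Nothing in the documents suggests that settings change between sessions.
- *That a burn would be mistaken for an injection-site effect of the study drug.* Protocol section 7.1.2 requires the investigator to assess causality and lists study procedure as a possible cause. The baseline test also takes place before dosing.
- *That section 9.2.3 lacks a needed lower limit.* It leaves the cold tests to the device programme, Attachment 4 gives 0°C, and the SAP uses 0°C. There is no conflict at that end.
- *That exposure can be sized by counting all planned heat ramps.* Only ramps still running at 50°C are affected, and their number is not given.

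**Conclusion.** This is an internal inconsistency in current protocol text and it should be corrected. The one automatic heat limit is stated as both 53°C and 50°C: a gap of 3°C, or 3 s at the stated ramp. The SAP exclusion rule agrees with Attachment 4 alone. If section 9.2.3 describes the actual setting, heat-pain thresholds measured from 50 to 53°C would be discarded under a reason that does not fit them.

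The conclusion rests on reading both sentences as the cut-off of the same device in the same test, which their wording supports. The sizes rest on the 32°C start and 1°C/s ramp given in both places. The number of ramps affected is unknown, and so is the temperature actually programmed. No view is taken on which value is right.

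**What to change.** The sponsor and the site should confirm the upper cut-off actually programmed on the TSA-II. Section 9.2.3 and Attachment 4 should then be reconciled so that one upper value stands in both. The SAP exclusion rule in section 5.7.4.1 and the reason used in the table in section 5.7.4.2 should be checked against that value, so that dropped readings are described as what they are.

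The cost is a short text correction in the protocol, a check of the device configuration, and a possible wording change in the SAP. No visit, test or data item is added.
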